Sample Size Determination: This study is powered based on the endpoint of cognitive deterioration at 3 months post-SRS, defined as decline of greater than 1 standard deviation (SD) from baseline on at least 1 of the neurocognitive tests. This was the primary endpoint of the Alliance N0574 study. With 60 accrued patients

and assuming a 20% drop-out rate, we will have sample size $n=48$. We have 85% power to detect a change in the cognitive deterioration rate from 64% in standard SRS to 42.5% in the current cognitive-sparing study with $n=48$ (Fisher's exact 2-group binomial test, 2-tailed $\alpha=0.05$).

4. Risks

The anticipated risk to patients in this study is minimal.

The MRI scans to be obtained at baseline would be added on to the same scan performed for routine SRS planning for patients. Follow up MRI would be standard of care imaging and would be obtained regardless of whether the patient is on or off study. These scans do not involve any radiation exposure. There are no additional risks associated with the research scans aside from discomfort due to the additional 8-10 minutes of scan time required. However, these scans are frequently performed as part of standard of care during presurgical planning without adverse effects. Some patients may experience claustrophobia in the MR scanner and may require the use of medications for this, as is prescribed routinely for brain MRIs when indicated.

Intracranial SRS would be performed identically to standard of care, except for adding additional regional avoidance for cognitive sparing. In cases where sparing of these structures cannot be performed without sacrificing treatment of the tumor or another critical structure, this will be recorded and the default will be the standard clinical plan. While clinical benchmarks of SRS quality will not be sacrificed on this study, there is a possibility that changing the SRS plan to achieve cognitive sparing may change the dose distribution to other structures in the brain. It is unclear whether this would change any clinical outcomes since SRS plans must adhere to the same rigorous standards as the current standard of care.

The directed neurocognitive evaluations are not standard of care unless a patient requires clinical referral to neuropsychology. Neuropsychological testing as described above is done verbally one-on-one with a licensed neuropsychologist. This is a 30 minute testing session that is frequently employed in clinical trials. One possible risk to neurocognitive testing is a possible increase in psychological strain in susceptible individuals (e.g., to the extent that thinking about their cognitive difficulties is stressful, patients might experience stress in being evaluated). However, these neurocognitive evaluations are designed to be non-stressful and to be used for patients who may have cognitive difficulties. Patients will be counseled that the testing is merely to assess particular functioning (short term memory, attention, etc) and that this would not affect their clinical care. These tests are not anticipated to be particularly stressful in any way and patients can stop the testing at any time. Patients may find it stressful to know whether they have deficiencies in their neurocognitive functioning. They can request to discuss this with the PI or neuropsychologist if they wish.

As mentioned, all imaging and neuropsychological data will be kept in a file that will not contain patient-identifying information. Thus, the risk for a breach of confidentiality is minimal. Moreover, the data will be stored in password-protected files only on the computers of investigators directly involved in the research.

5. Privacy and Confidentiality

Confidentiality of a subject's protected health information will be maintained by the following methods: study-specific records containing protected health information, and copies of study-related medical records, will be kept in locked filing cabinets at the Moores UCSD Cancer Center locked research administrative offices (Clinical Trials Office).

Computers containing access to protected health information will have password-access; and screen-savers will be utilized to prevent unauthorized viewers from inadvertently seeing information. Protected health information will be stored on secure servers. The servers supporting these studies are located inside a locked rack within the San Diego Supercomputer data center. The facility features restricted access by means of personal codes (PINs) and biometrics, and is monitored 24 hours a day 7 days a week. The electrical power is backed up by battery-powered uninterruptible power supplies, as well as by on-site generators. Both servers are behind firewalls configured to allow access only to credentialed personnel within the UCSD network. Velos, the clinical

trials management system, maintains an additional internal access control mechanism via user names and passwords. Data transactions executed over our intranet are encrypted via Secure Sockets Layer.

Access to a subject's protected health information will be limited to those study personnel who need to use it to accomplish the purpose of the research, and the minimum necessary information to accomplish the purpose of the research will be collected, stored, used, and reported. When protected health information is sent outside the University of California, San Diego, it will be disclosed only to those parties listed in the subject's authorization, and an audit trail log will be maintained of what information was sent and to whom it was sent.

Patients will be assigned a random study identification number for purposes of organizing the data and the data for the study will be kept in 2 main files: the "central" file and the "code" file. After the data is collected, it will be stored in the "central" file (that will contain no patient-identifying information such as name, date of birth, MRN, etc.). A separate, password-protected "code" file will contain the mappings of patient name with their random study identification number. This file will be password-protected, with the password known only to CITI-trained study personnel, and it will be stored exclusively on the computer of the principal investigator. These patient identifiers will be destroyed following the collection and aggregation of the dataset, and thus the patient data will be officially de-identified at this time.

Subject identifiers will be destroyed by the PI at the earliest opportunity consistent with the conduct of the research, unless there is a health or research justification for retaining the identifiers or such retention is required by law.

6. Data Safety and Monitoring

Personnel responsible for the safety review and its frequency

The principal investigator will be responsible for monitoring the data, assuring protocol compliance, and conducting the safety reviews at the specified frequency which must be conducted at a minimum of every 6 months (including when re-approval of the protocol is sought). During the review process, the principal investigator will evaluate whether the study should continue unchanged, require modification/amendment, continue or close to enrollment. The principal investigator has the authority to stop or suspend the study or require modifications. This study has been approved by the UCSD Institutional Review Board.

Attribution of Adverse Events

Adverse events will be monitored for each subject participating in the study and attributed to the study procedures by the principal investigator according to the following categories:

Definite: Adverse event is clearly related to investigational procedures

Probable: Adverse event is likely related to investigational procedures

Possible: Adverse event may be related to investigational procedures

Unlikely: Adverse event is likely not to be related to the investigational procedures
Unrelated: Adverse event is clearly not related to investigational procedures

Plan for Grading Adverse Events

Adverse events noted during the study will be graded using the NIH Common Toxicity Criteria for Adverse Events scale (CTC), version 4.0 (<http://evs.nci.nih.gov/ftp1/CTCAE/About.html>). Specific conditions and symptoms may have values or descriptive comment for each level, but the general guideline is:

1 - Mild

2 - Moderate

3 - Severe

4 - Life threatening

5 - Death

Plan for Determining Seriousness of Adverse Events

In addition to grading the adverse event, the PI will determine whether the adverse event meets the criteria for a Serious Adverse Event (SAE). An adverse event is considered serious if it:

1. Is life-threatening

2. Results in in-patient hospitalization or prolongation of existing hospitalization
3. Results in persistent or significant disability or incapacity
4. Results in a congenital anomaly or birth defect
5. Results in death
6. Based upon appropriate medical judgment, may jeopardize the subject's health and may require medical or surgical intervention to prevent one of the other outcomes listed in this definition
7. Adversely affects the risk/benefit ratio of the study

An adverse event may be graded as severe but still not meet the criteria for a Serious Adverse Event. Similarly, an adverse event may be graded as moderate but still meet the criteria for an SAE. It is important for the PI to consider the grade of the event as well as its "seriousness" when determining whether reporting to the HIC or HSC is necessary.

Plan for reporting serious AND unanticipated AND related adverse events, anticipated adverse events occurring at a greater frequency than expected, and other unanticipated problems involving risks to subjects or others

The principal investigator will report the following types of adverse events to the HIC, and to any and all co-investigators:

- a) Serious AND unanticipated AND possibly, probably or definitely related events
- b) Anticipated adverse events occurring with a greater frequency than expected
- c) Other unanticipated problems involving risks to subjects or others.

These adverse events or unanticipated problems involving risks to subjects or others will be reported to the HIC within 48 hours of it becoming known to the investigator, using the appropriate forms found on the website.

The principal investigator will conduct a review of all adverse events upon completion of every study subject. The principal investigator will evaluate the frequency and severity of the adverse events and determine if modifications to the protocol or consent form are required.

7. References

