Radiation Planning Dose Constraints: As of yet, there are no evidence-based dose constraints for cognitive-sparing in brain SRS. Rational dose tolerances in clinical trials (a dose which predicts a particular likelihood of dysfunction) must be calculated based on normal tissue complication probability (NTCP) analyses⁷⁸. Hippocampal dose constraints used in WBRT trials²⁵ are not relevant to SRS (where high ablative doses are delivered) given that the prescription dose is so low in WBRT (30Gy in 10 fractions). In another IRB-approved longitudinal, prospective, observational study of primary brain tumor patients receiving definitive fractionated radiotherapy, we have been prospectively tracking domain-specific cognitive decline with all the standard cognitive measures in Table 1. Based on preliminary NTCP analyses from 28 patients, we found that maximum dose to the left hippocampus >28Gy (in 30 fractions) predicted for a >10% risk of significant decline (reliable change index <90% confidence interval) in HVLTR total and HVLTR delayed memory scores (p=0.01). Conversion of this maximum dose to a single fraction SRS dose constraint based on the linear quadratic formalism with $\alpha/\beta=2.5$ Gy for normal brain tissue yields a hippocampal maximum dose of 8.4Gy. This conversion was performed by solving for isoeffective dose by equating biologically effective doses from SRS single-fraction treatment, D_{SRS} , and reference fractionation, dose D_{ref} , delivered in N_{ref} fractions (set to 30):

$$D_{ref} \left(1 + \frac{D_{ref}}{\alpha/\beta} \right) = D_{SRS} \left(1 + \frac{D_{SRS}}{\alpha/\beta} \right)$$

For white matter tracts, within the left parahippocampal cingulum, V45Gy at 20.6% was predictive of significant decline on HVLTR total and HVLTR delayed memory scores (p=0.001). Conversion of this to a single fraction SRS dose constraint with $\alpha/\beta=2.5$ Gy for normal brain tissue (same method as above) yields a white matter maximum dose of 12Gy. Furthermore, a recently published analysis of SRS dose tolerances for the optic pathway (another critical white matter tract) established 12Gy in 1 fraction maximum dose as resulting in <1% risk of radiation-induced optic nerve neuropathy, supporting this white matter constraint. Dose constraints for single fraction SRS are summarized in Table 3. For lesions receiving 3 fractions, isoeffective dose constraints from Table 3 will be calculated based on $\alpha/\beta=2.5$ Gy.

Table 3: Dose Constraints

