Eloquent Cognitive Structures	Max Dose (Gy)
Cingulum	12
Uncinate Fasciculus	12
Inferior longitudinal fasciculus	12
Corpus Callosum	12
Arcuate fasciculus	12
Inferior frontostriatal tracts	12
Fornix	12
Hippocampus	8.4

*all bilateral except Corpus Callosum

SRS planning, plan optimization, and treatment: Patients will undergo setup, immobilization and simulation for frameless linear accelerator-based intracranial SRS with non-coplanar volumetric modulated arc radiosurgery (VMAR) as previously described⁷⁹. White matter and hippocampal 3D segmentations will be imported into the Eclipse treatment planning software (Varian Medical Systems, Palo Alto, California) for each patient. High-resolution, distortion-corrected stereotactic-protocol contrast-enhanced T1-weighted images will be co-registered with CT. Target volumes (enhancing tumor + 1mm margin for planning target volume, PTV) and standard organs at risk (OARs), such as the brainstem, optic nerves, and optic chiasm, will be manually contoured by the treating radiation oncologist. Tolerance doses for SRS planning include the white matter and hippocampal doses above, and standard single fraction dose constraints for other OARs as previously published⁸⁰. Prescription doses to each target lesion will be based on volume: 24 Gy in a single fraction if the target is less than 1 cc, 22Gy for 1.1-4cc target, and 20Gy for those between 4.1-10cc. For larger lesions or tumor beds, fractionated SRS with 24Gy in 3 fractions will be used respecting the constraints above. These doses closely follow a large Japanese SRS study²² with modern target volume-based doses, and are also similar to the Alliance N0574 trial⁵.

Automated knowledge-based brain SRS plans will be generated as previously described⁶⁹, with dose optimized within standard clinical guidelines (98% of the PTV receiving 100% of the prescription dose^{34,36}) and tolerance OAR doses above. Dose volume histograms will be assessed and re-optimized if necessary, without compromising coverage of tumor or sparing of standard critical structures (i.e. brainstem, optic structures.). All plans will be reviewed by the PI and the UCSD CNS Radiosurgery team for approval. Treatment delivery will follow the UCSD standard frameless brain SRS protocol⁷⁹.

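### The 8.4 Gy hippocampal limit does not follow from its stated derivation: 28 Gy in 30 fractions at alpha/beta 2.5 Gy converts to 8.63 Gy

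*Protocol*

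**What the plan says.** The section Radiation Planning Dose Constraints starts from preliminary normal tissue complication analyses in 28 patients. There, "maximum dose to the left hippocampus >28Gy (in 30 fractions") predicted a risk above 10% of significant decline in two verbal memory scores. The protocol converts this dose to a single fraction with the linear quadratic model at alpha/beta 2.5 Gy for normal brain. It describes the method in words: "This conversion was performed by solving for isoeffective dose by equating biologically effective doses" of the single-fraction treatment and the reference schedule, with the number of reference fractions set to 30. The conversion, it says, "yields a hippocampal maximum dose of 8.4Gy".

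Table 3 lists 8.4 Gy for the hippocampus. The figure is then used in two ways:

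- as a planning limit, under SRS planning, plan optimization, and treatment: "Tolerance doses for SRS planning include the white matter and hippocampal doses above";
- as the source of the fractionated limit: "For lesions receiving 3 fractions, isoeffective dose constraints from Table 3 will be calculated" with alpha/beta 2.5 Gy. Larger lesions or tumor beds are the ones treated this way: "fractionated SRS with 24Gy in 3 fractions will be used respecting the constraints above".

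**The concern.** All the inputs to the conversion are stated, so it should reproduce to the one decimal printed. It does not.

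The derivation matters because the hippocampal limit has no other support in the document. The section sets aside the hippocampal constraints from whole brain trials as not relevant to radiosurgery. The 12 Gy white matter limit has a second argument, a published optic pathway analysis; the hippocampal limit has none. Its link to the stated memory risk rests on this one conversion.

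The relation of 8.4 Gy to the dose tied to that risk is therefore unclear. If every stated input is right, 8.4 Gy lies 0.23 Gy below the equivalent of the reference dose. If one input is misprinted and the conversion was actually run to 8.4 Gy, the two are equal. The reader cannot tell which.

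**Working it through.** **Inputs** (all from Radiation Planning Dose Constraints): reference dose D_ref = 28 Gy; N_ref = 30 fractions; alpha/beta = 2.5 Gy; rule: equal BED.

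**Formula.** In words the rule is BED(reference) = BED(single fraction), that is

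D_ref × (1 + D_ref / (N_ref × alpha/beta)) = D × (1 + D / (alpha/beta)),

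which solves to D = [−alpha/beta + √((alpha/beta)² + 4 × alpha/beta × BED)] / 2.

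The equation as it appears in the text has no N_ref term on the reference side, although N_ref is defined just before it. The term may have been lost in conversion from PDF, and its absence is not counted here as an error. Taken literally, that equation returns D = D_ref = 28 Gy, so it does not lead to 8.4 Gy either. The check uses the rule as worded.

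**Attempt to reproduce 8.4 Gy**

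- BED = 28 × (1 + 28/75) = 38.45 Gy
- D = [−2.5 + √(6.25 + 10 × 38.45)] / 2 = **8.63 Gy**
- Gap: 8.63 − 8.4 = 0.23 Gy, or 2.8% of 8.4 Gy

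**Check that the rule is read correctly.** The protocol applies the same method to 45 Gy for white matter and states 12 Gy. In 30 fractions, BED = 45 × (1 + 45/75) = 72 Gy and D = 12.22 Gy, which is 12 to the nearest Gy. The same reading thus works for white matter and fails for the hippocampus.

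**Can rounding explain it?**

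| Reference dose | alpha/beta | Single-fraction dose |
|---|---|---|
| 28 Gy | 2.5 | 8.63 Gy |
| 27.5 Gy | 2.5 | 8.52 Gy |
| 28 Gy | 2.45 | 8.58 Gy |
| 27.5 Gy | 2.45 | 8.47 Gy |

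The last row takes both inputs at the lowest values that round to the printed ones, and it still prints as 8.5. Going through the equivalent dose in 2 Gy fractions changes nothing (8.63 Gy), and rounding that intermediate to 21 Gy gives 8.55 Gy.

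**What would give 8.4 Gy?** Its BED is 8.4 × (1 + 8.4/2.5) = 36.62 Gy. Changing one input at a time, this needs one of:

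- a reference dose of about 26.9 Gy in 30 fractions;
- alpha/beta of about 2.27;
- about 36 reference fractions.

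None of these is stated.

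**Effect on the 3-fraction limit** at alpha/beta 2.5 Gy, solving D × (1 + D/7.5) = BED:

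- from the printed 8.4 Gy (BED 36.62): 13.24 Gy
- from the stated inputs (BED 38.45): 13.64 Gy
- gap: 0.40 Gy, or 3.0%

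**The case against.** The strongest reply is that this has little practical effect. Planners get one instruction, since 8.4 Gy appears in both the text and Table 3. On the stated inputs the printed limit is the lower figure, so nothing shows that patients would exceed an intended tolerance. The reference threshold comes from a preliminary analysis of 28 patients and is not presented as precise to 3%. Sparing also gives way to other aims: plans are re-optimized "without compromising coverage of tumor or sparing of standard critical structures", and Standard of Care Treatment Procedures falls back to the standard plan where sparing would cost too much. All of this stands, and it is why the point is rated minor.

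A second reply is that the limits may have been set deliberately on the low side, since 12 Gy is also below its computed 12.22 Gy. In that case no printed number would be wrong and only the description would be incomplete. The document cannot exclude this, but it mentions no margin or downward adjustment and presents 8.4 Gy as the result of the conversion. The 12 Gy figure is ordinary rounding to the nearest Gy; 8.4 is not a rounding of 8.63. If such a step was taken, it needs to be written down.

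A third reply is that 8.63 Gy rests on the worded rule and not on the equation as it appears. That is true. The wording is explicit, however, the white matter figure supports it, and the equation without N_ref cannot give 8.4 Gy.

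**Conclusion.** The concern holds. On the worded equal-BED rule with 28 Gy, 30 fractions and alpha/beta 2.5 Gy, the single-fraction equivalent is 8.63 Gy, not 8.4 Gy. Either one of the printed figures is misstated or a step is missing from the description, and the document does not show which. The difference is 0.23 Gy (2.8%) for one fraction and 0.40 Gy (3.0%) for three.

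The severity is minor. The printed limit is consistent in itself, and the sample size, endpoint and primary test are untouched. This finding takes no view on which limit is right.

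**What to change.** Reconcile the reference dose, number of fractions, alpha/beta and Table 3 hippocampal value so that the stated derivation reproduces the stated limit. Confirm that the equation shows the fraction number. If a margin or other adjustment was applied, say so. Then derive the 3-fraction limit from the reconciled figures with the same alpha/beta. The choice of value belongs to the sponsor's physicists and clinicians.

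The cost is a physics re-check and a short amendment to Radiation Planning Dose Constraints. What else changes depends on the cause:

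- If only the reference dose or fraction number is corrected, Table 3 and the 3-fraction limit stay as they are.
- If alpha/beta is corrected, the 3-fraction conversions need checking, because they use the same 2.5 Gy for every structure, and so does the white matter conversion.
- If the Table 3 value is corrected, the hippocampal planning objective and its 3-fraction equivalent must be updated.

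No statistical section needs to change.

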Neuropsychological data: A well-established, well-validated, battery of neurocognitive tests will be performed prior to SRS and 3-months following SRS to evaluate different neurocognitive domains including verbal memory, executive functioning, attention/processing speed, and language. These are shown in Table 2. This cognitive battery takes 30 minutes to perform. This core battery is frequently employed in large-scale clinical trials, including Alliance Trial N0574⁵, because the tests are brief, repeatable, have good psychometric properties, and have been shown to be sensitive to cognitive decline in patients with metastatic brain tumors⁷⁰. Most tests have several alternate forms, making them ideal for repeat measurements. Health-related quality of life will also be assessed. Since depression may also influence test scores^{71,72}, we will administer the Beck Depression Inventory (BDI)⁷³ at each evaluation to screen for depression and include the BDI score as an additional covariate. All cognitive testing will be performed by a trained, certified neuropsychologist.

Table 2. Neurocognitive Domains and Tests

Cognitive Domain	Neuropsychological Test
Verbal Memory	
 Hopkins Verbal Learning Test–Revised (HVLTR); Immediate, Delayed Recall
Executive Functioning	
 Controlled Oral Word Association Test (COWA): letter fluency Trail Making Test Part B (TMT-B)
Attention/Processing Speed	
 Trail Making Test Part A (TMT-A)
Language	
 Boston Naming Test (BNT) Controlled Oral Word Association Test (COWA): category fluency
Mood	
 Beck Depression Inventory (BDI)
Quality of Life	
 Functional Assessment of Cancer Therapy-Brain (FACT-BR)

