Patients will be seen by the treating physician on the day of SRS, and on subsequent follow-up visits. They will be followed closely with clinical and imaging exams for safety and tumor recurrence (i.e., 1 month, 3 months, 6 months post-SRS). All treatment-related toxic effects and adverse events will be recorded according to NCI Common Terminology Criteria for Adverse Events, version 4.0. Local tumor control rates for each treated lesion will be assessed according to the revised Response Assessment in Neuro-oncology (RANO) criteria^{81,82}.

Payment

Parking for study patients related to study visits will be complementary. Subjects will be compensated \$100 for participation in this study to help compensate for time and travel costs.

Statistical Considerations

Primary Objective Analysis:

Cognitive test results (pre- and post-SRS) will be scored based on standardized published norms^{72,87}. Cognitive deterioration will be defined as a decline of greater than 1 SD on at least 1 of the 7 cognitive tests (Table 2, not including BDI or FACT-BR). Fisher's exact 2-group binomial test will be used to compare the proportion of patients with 3-month post-SRS cognitive deterioration between the current cognitive-sparing SRS study and previously reported with standard SRS.⁵ Further analyses of pre- to post-SRS cognitive change for each test will

utilize a reliable change index (RCI)⁸⁷. This index is derived from the standard error of measurement of each test, and it represents the 90% confidence interval (CI) for the difference in raw scores from baseline to follow-up that is expected if no real change has occurred. RCI values below the 90% CI are indicative of significant decline. RCIs also account for practice effects, which is ideal for this study where evaluations are 3 months apart. One-sample t-tests ($H_0=0$) will be used to determine significant group decline in RCIs by test and cognitive domain. Pearson correlation coefficients will be used to assess associations between RCIs and depression scores. Bonferroni corrections will be applied to control for Type I errors due to multiple comparisons.

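### Bonferroni for the supportive RCI tests is valid, but Holm's step-down gives the same error control and never rejects less: a minor, free improvement

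*Protocol*

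**What the plan says.** Under Statistical Considerations, Primary Objective Analysis, the protocol first defines the primary endpoint as a "decline of greater than 1 SD on at least 1 of the 7 cognitive tests" and compares the resulting proportion with the historical one by a single Fisher's exact test.

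It then turns to the RCI under the words "Further analyses of pre- to post-SRS cognitive change for each test will". One-sample t-tests against zero "will be used to determine significant group decline in RCIs by test and cognitive domain". Next, "Pearson correlation coefficients will be used to assess associations between RCIs and depression scores". The paragraph closes with "Bonferroni corrections will be applied to control for Type I errors due to multiple comparisons".

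No step-down version is named, and the family or families to be corrected are not defined. The section Neuropsychological data lists four cognitive domains: "verbal memory, executive functioning, attention/processing speed, and language". In Table 2, three of them hold two measures each, and attention/processing speed holds TMT-A alone. On sample size, the protocol states: "assuming a 20% drop-out rate, we will have sample size $n=48".

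**The concern.** The protocol itself names the adjustment, so this is a stated choice rather than a detail left open. Read naturally, it means that every p-value in a family of m is compared with alpha/m. Holm starts at the same threshold and relaxes it after each rejection. It needs no extra assumption and cannot lose a finding that Bonferroni would make.

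The usual reason to prefer Bonferroni is that it gives simple simultaneous confidence intervals. That reason is absent here: no such intervals are planned for mean RCI, and the 90% interval in the text is the reliable-change band for an individual patient.

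At stake is how completely the trial can say which functions declined, with only 48 evaluable patients expected.

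**Working it through.** **Plan's own figure.** The protocol gives no power or adjusted level for the RCI tests, so there is nothing to reproduce. Its 85% power belongs to the primary endpoint, which this point does not touch.

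**Inputs from the protocol**
- Evaluable patients: 60 × (1 − 0.20) = 48 (Sample Size Determination).
- Test-level RCIs: 7, from HVLT-R immediate and delayed recall, COWA letter fluency, TMT-B, TMT-A, BNT and COWA category fluency (Table 2).
- Domains: 4 (Table 2).

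**Assumptions, not in the protocol**
- Family-wise level 5%, two-sided. The protocol states this level for the primary endpoint only.
- Correlation between tests 0.3, varied to 0 and 0.5.
- Standardised mean decline in RCI of 0.2 to 0.5 SD.
- A family of the 7 test-level RCIs.

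**Thresholds for m = 7**
- Bonferroni: every p-value against 0.05/7 = 0.00714.
- Holm: ordered p-values against 0.05/7, 0.05/6, ..., 0.05/1, that is 0.00714, 0.00833, 0.0100, 0.0125, 0.0167, 0.025, 0.05, stopping at the first failure.

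Every Holm threshold is at least 0.00714, so any hypothesis that Bonferroni rejects is also rejected by Holm. The first threshold is the same, so the probability of at least one rejection is identical.

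**Bonferroni level, direct check.** At 0.4 SD the noncentrality is 0.4 × √48 = 2.77. The two-sided critical value at 0.00714 with 47 degrees of freedom is 2.81, and the power is 49%. This agrees with the simulation below.

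**Average power per truly declining test** (simulation, n = 48, 7 tests, correlation 0.3)

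| Scenario | Bonferroni | Holm |
|---|---|---|
| All 7 decline 0.5 SD | 74% | 86% |
| All 7 decline 0.4 SD | 49% | 61% |
| All 7 decline 0.3 SD | 24% | 30% |
| All 7 decline 0.2 SD | 8.6% | 9.8% |
| 4 of 7 decline 0.4 SD | 49% | 53% |
| 3 of 7 decline 0.4 SD | 49% | 52% |
| 2 of 7 decline 0.4 SD | 49% | 50% |
| 1 of 7 declines 0.4 SD | 49.6% | 49.7% |

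The correlation matters little. With all seven at 0.4 SD the change is 48.9% to 60.2% at correlation 0, and 49.3% to 60.3% at correlation 0.5.

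**Any rejection.** With all seven at 0.4 SD and correlation 0.3, it is 94% under both methods.

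**Family-wise error.** With no true effects it is the same for both: 4.9% at correlation 0 and 3.8% at correlation 0.5. With four of seven real and correlation 0.3, Holm's error is 3.2%, below 5%. In no simulated trial did Holm miss a hypothesis that Bonferroni rejected.

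**If tests and domains are pooled.** This gives 7 + 4 = 11 comparisons. Suppose each domain RCI is the mean of its tests, which the protocol does not say. A mean of two tests at correlation 0.3 has variance (1 + 0.3)/2 = 0.65, so a 0.4 SD decline becomes 0.4/√0.65 = 0.50 SD. The attention/processing-speed domain is TMT-A again. Average power is then about 50% (Bonferroni) against 61% (Holm), a gain similar to that for seven tests. In this reading TMT-A uses two of the eleven shares of alpha.

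**The case against.** Bonferroni is a valid procedure. Nothing in the section is false or contradictory, and the choice concerns supportive analyses only. The text says only that Bonferroni corrections will be applied, so that it means the plain single-step form is inferred, and an analysis plan could still refine it. All of this stands, and it limits the point to one of efficiency.

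The larger gains also need decline across the whole battery. If one to three tests decline, the pattern for which test-by-test inference is most useful, the gain is 0 to 3 points. This stands too.

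Three stronger readings may tempt a reader, and the protocol does not support them:

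- **The lost power makes the technique look safer than it is.** Both methods have the same chance of finding some decline, and the per-patient deterioration rate that forms the primary endpoint is untouched. Holm only adds further rejections after the first.
- **TMT-A is tested twice at the cost of alpha.** This holds only if tests and domains form one family. The wording could equally mean one family of seven and another of four, and then the overlap adds no test to the family of seven.
- **The domain tests should be reduced to summaries.** That would remove planned inference, although domain-specific cognitive outcomes appear in the protocol's second primary objective. It would also leave unclear where the correlations with depression scores belong. Changing to Holm requires neither step.

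**Conclusion.** The point holds as a minor, free improvement. That Holm controls the same family-wise error under any dependence and never rejects less than Bonferroni is a general result, independent of this trial's data. The size of the gain is not: under the assumptions listed it runs from essentially zero with one affected test, through about 4 points with four of seven at 0.4 SD, to about 12 points with all seven at 0.4 or 0.5 SD. The primary comparison, its alpha and the sample size are unaffected. The protocol's Bonferroni correction is not an error and would not invalidate any result.

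**What to change.** In Primary Objective Analysis, name a Holm step-down adjustment in place of the Bonferroni corrections, applied within each family where a correction is intended. Keep the planned test-level and domain-level RCI tests and the correlations with depression scores. If tests and domains are placed in one family, count TMT-A once, since in Table 2 it is the whole attention/processing-speed domain.

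The change takes a phrase, and a second sentence if the families are pooled. It needs no extra patients, data or visits. The only thing given up is the simple form of Bonferroni's simultaneous confidence intervals, which this protocol does not plan to use for mean RCI.
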